- For a missing first period double-blind medication end date, if an End of Treatment (EoT) visit is documented only, then the date of the EoT visit will be used. If a Visit 11 is documented only, or is documented along with an EoT visit or a Visit 15, then the date of Visit 11 will be used.
- If the first period double-blind medication end date is incomplete with the month and the year present, and the EoT visit and Visit 11 are missing, then the first day of the following month will be used.
- For a missing second period double-blind medication end date, if an EoT visit is documented (in addition to Visit 11), then the date of the EoT visit will be used. If a Visit 15 is documented (in addition to Visit 11), then the date of Visit 15 will be used.
- If the second period double-blind medication end date is incomplete with the month and the year present, and the EoT visit and Visit 15 are missing, then the first day of the following month will be used.
- If the patient is lost to follow up, or continues in the trial without the expected visit for imputation being available at all (e.g. Visit 11 is missing, but Visit 12 and/or Visit 15

present), then the date of the previous double-blind drug dispensing visit + longest possible treatment duration based on drug supply at that visit + 1 day will be used.

- If the ramipril end date is missing, then the date of the previous ramipril dispensing visit + longest possible treatment duration based on drug supply at that visit + 1 day will be used.
- If the ramipril end date is incomplete with the month and year present, then the first day of the following month will be used.
- If a patient died during the course of the trial and no additional information about drug stop date(s) is (are) available, then the date of death will be used as drug stop date(s) assuming that the patient took the medication(s) until the day of death.
- All other cases need to be assessed by the trial team on an individual basis, trying to use the points above as guidance.

If only the year of birth is known, the day and month of birth will be imputed as 01 January.

For partial start and stop dates for concomitant therapies (CT) the following derivations will be used to impute 'worst case' values:

- If the day of the end date is missing then the end date is set to last day of the month.
- If the day and month of the end date are missing then end date is set to 31 December of the year.

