- If the day of the start date is missing the start date is set to first day of the month.
- If the day and month of the start date are missing then the start date is set to 01 January of the year.

For other incomplete date information the midpoint of the possible interval will be used. If only the year is present, the day and month will be imputed as 01 July. If year and month is present the day will be imputed as 15. If the year is missing, the date will be considered missing.

All other cases need to be assessed by the trial team on an individual basis, using the above points as guidance.

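### A ramipril stop date known only to the month is imputed as the first of the next month, even when the final visit is documented

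*SAP*

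**What the plan says.** All the rules are in SAP section 6.6.3.

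- **Ramipril, month known:** "If the ramipril end date is incomplete with the month and year present, then the first day of the following month will be used". No condition or upper limit is attached.
- **Ramipril, date fully missing:** "If the ramipril end date is missing, then the date of the previous ramipril dispensing visit" is the starting point. The longest time the dispensed supply could last and one further day are added. No end visit is consulted.
- **Double-blind drug, date missing:** the documented end visit is used. For period 2, for example: "If a Visit 15 is documented (in addition to Visit 11), then the date of Visit 15 will be used".
- **Double-blind drug, month known:** the next-month rule applies only as a fallback. For period 1 the condition is "and the EoT visit and Visit 11 are missing, then the first day of the following month will be used", and for period 2 "and the EoT visit and Visit 15 are missing, then the first day of the following month will be used".
- **Lost to follow-up, or continuing without the expected visit:** a separate bullet uses dispensing date plus supply plus one day. Its own example is Visit 11 missing with Visit 12 or 15 present.
- **Death, with nothing else known about the stop date:** date of death, "assuming that the patient took the medication(s) until the day of death".

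Other partial dates stay inside the known month. For concomitant therapy, under a rule the SAP itself calls worst case: "If the day of the end date is missing then the end date is set to last day of the month". For remaining incomplete dates: "If year and month is present the day will be imputed as 15".

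**The concern.** A record that ramipril stopped in March rules out 1 April, yet 1 April is what the rule assigns. This is not a convention of recording the day after the last dose: Table 6.1: 1 defines periods by last intake or last administration, and the death bullet assumes intake up to the stop date.

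The SAP is also uneven between drugs. It trusts a documented Visit 11, Visit 15 or EoT for a missing double-blind end date, but never for ramipril. An imputed ramipril date can then fall after the final visit or last contact. It can also fall after death, because the death bullet, as worded, gives way once any other information on the stop date exists, and a recorded month is such information.

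At stake are whole-trial ramipril exposure (section 7.7) and, for patients never given double-blind drug, the end of run-in. Table 6.1: 1 sets that end at last ramipril intake plus x, with x = 7 days for adverse events and 3 for laboratory data. For double-blind drug the stop date feeds exposure, the same kind of windows, and the washout length behind deviation G3.47.

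**Working it through.** The plan states no figure on this point, so there is none to reproduce. The check is calendar arithmetic.

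**1. Size of the overstatement.** For a true stop on day d of a month with L days, the next-month rule overstates by L + 1 − d days and a month-end rule by L − d. Means give each day equal weight, which is an assumption.

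| Month length | Next-month rule | Month-end rule |
|---|---|---|
| 28 days | 1 to 28, mean 14.5 | 0 to 27, mean 13.5 |
| 30 days | 1 to 30, mean 15.5 | 0 to 29, mean 14.5 |
| 31 days | 1 to 31, mean 16.0 | 0 to 30, mean 15.0 |
| 365-day year | 1 to 31, mean 15.7 | 0 to 30, mean 14.7 |

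Moving to month-end recovers exactly 1 day. The rest can be recovered only by using visits and other known limits.

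**2. Ramipril exposure.** Table 6.7: 2 plans four phases of 28 days, so 4 × 28 = 112 days. The extreme overstatement is 31/112 = 27.7%, and the mean is 15.7/112 = 14.0%. In the extreme case 112 − 31 = 81 true days would be counted as 16 weeks. This requires a stop on day 1 of a 31-day month.

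**3. A documented final visit is ignored.** Suppose last intake and Visit 15 are both on 10 March and the stop is recorded as March. The imputed date is 1 April, which is 31 + 1 − 10 = 22 days after the visit.

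**4. Patient never given double-blind drug.** With last ramipril intake on 10 March, the adverse event window should end on 17 March (10 + 7) and the laboratory window on 13 March (10 + 3). With 1 April imputed they end on 8 April and 4 April, each 22 days late.

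**5. Fully missing ramipril date.** The error depends on the supply dispensed, which the SAP does not state, so it is not quantified.

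**6. Period 1 double-blind drug, only if the next-month bullet prevails.** Let w be the true number of days from last period 1 dose to first period 2 dose. The window reaches period 2 when L + 1 − d + x ≥ w. With the planned w = 28, counting stop days over a 365-day year:

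- x = 0: 41 of 365 (11%); x = 7: 125 of 365 (34%).
- Apparent washout below 14 days, a false G3.47: 197 of 365 (54%).
- Month-end rule instead: 29, 113 and 185 of 365.

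At the washout window limits, w = 15 gives 54% (x = 0) and 77% (x = 7), and w = 42 gives 0% for both. These are shares of calendar days, not of patients.

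**7. Capping the period 1 stop date alone is not enough.** Take a true stop on 1 March with period 2 starting 29 March. The rule gives 1 April; adding 7 days gives 8 April, which is 11 days inside period 2 (29 March to 8 April). Capping the stop at 28 March still leaves almost no apparent washout. The window then runs to 4 April, 7 days inside period 2. The window itself must be truncated.

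**The case against.** The strongest reply is that the reach is narrow and the choice deliberately over-inclusive. Much of this stands.

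- **Double-blind drug.** A reader might infer that every study-drug stop date ignores the final visit. The text does not support that: the double-blind next-month rules apply only when the end-of-period visit is missing. Only ramipril ignores a documented visit.
- **Overlapping crossover periods.** A reader might infer that events will be counted under both treatments. That needs a patient with Visit 11 and EoT both missing who still entered period 2, and the supply-based bullet names that situation. What is established is that two bullets apply, can give different dates, and have no stated order. The overlap figures hold only if the next-month bullet wins.
- **Run-in.** For patients given double-blind drug, run-in ends the day before period 1 whatever the ramipril end date, so their run-in windows do not move.
- **Consequences.** There is no per-protocol set and section 7 only lists deviations in the randomised period, so a false G3.47 excludes nobody. Week 4 GFR windows are anchored on first intake.
- **Convention.** Latest possible date plus one matches the plus-one-day supply rule. That explains the choice but does not make the date possible, and overstated exposure is not a cautious error. Sending unlisted cases to the trial team does not help, because these cases are listed.

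Nothing in the SAP shows that early stoppers are more likely to have partial dates, and this point does not rest on that.

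**Conclusion.** The point holds for ramipril. A partial end date is always set outside its recorded month, and a partial or fully missing one can pass the documented final visit, last contact or death. The overstatement is 1 to 31 days per partial date, about 15.7 days on average if stop days are evenly spread. The 28% figure is the extreme, not the typical size.

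For double-blind drug the fault is smaller. It is one day past month-end with no limit at last contact or death, and it arises only when the end visit is missing. For period 1 there is also an unresolved choice between two bullets.

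The effects are on descriptive exposure, on adverse event and laboratory assignment, and on a listed deviation. It would be wrong to infer damage to the GFR analysis. The conclusion assumes that a stop date means last intake, as the SAP's period table and death bullet indicate. How many of the 31 randomised patients, or of those treated in run-in only, have partial dates is not stated and may be none.

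**What to change.** Amend section 6.6.3 and Table 6.1: 1 as follows.

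1. **Partial study-drug stop date:** use the last day of the recorded month, truncated at the earliest of documented Visit 15/EoT (for ramipril), last contact and death, but never earlier than the first day of the recorded month. That floor matters when the recorded month is later than the visit; without it, truncation would again give a date the record excludes.
2. **Fully missing ramipril end date:** use Visit 15/EoT when documented, and dispensing date plus supply only otherwise, with the same limits.
3. **Precedence:** state which bullet applies to a partial period 1 end date when Visit 11 and EoT are missing but Visit 12 or 15 is present.
4. **Period 1 window:** end stop date plus x no later than the day before the first period 2 dose, and do not derive G3.47 from an imputed stop date without review.

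The cost is SAP wording and a few lines of derivation code. Slightly fewer events may count as on-treatment.

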## **6.7 BASELINE, TIME WINDOWS AND CALCULATED VISITS**

To avoid all ambiguity, the term “baseline” should not be used without further qualification. Measurements taken prior to the start of open-label ramipril treatment will be referred to as “screening baseline” (Visit 4). Measurements taken prior to randomisation to one of the two double-blind treatment sequences will be referred to as “randomisation baseline” (Visit 8).

Randomisation baseline will be at visit 8 and prior to intake of any double-blind study drug. If more than one value is recorded at visit 8, the value taken at timepoint -0:05 will be used. These will be referenced to explicitly within [Section 5.3](#) Further endpoints.

Period baseline is the baseline prior to intake of any double-blind study drug, within each of the two cross-over periods. For period 1, this is the same as randomization baseline. For period 2, this is prior to the intake of double-blind study drug in the second sequence of the cross-over. This value has not always been recorded, but is often available for laboratory data.

Time windows for visits will be defined in general relative to the start of the relevant treatment period (and not relative to the start of any treatment or to randomisation). The date and (where relevant) clock time of the first drug administration for that treatment period will be used to determine the visit windows. The notable exception to this is the washout period, which is defined based upon the date and time of the last intake of the first period double-blind medication.

Measurements taken prior to the first intake of any study medication (ramipril, empagliflozin or placebo) will be considered pre-treatment or screening values. Pre-treatment values will be assigned to a visit according to the nominal visit number as recorded on the eCRF or as provided by the laboratory. Measurements taken after the first intake of ramipril but before intake of double-blind medication will be considered run-in or randomization baseline values. Measurements taken after the last intake of the first double-blind medication but before the intake of the second double-blind medication will be considered washout values.

Measurements taken after the first intake of any study medication (ramipril, empagliflozin or placebo) will be considered on-treatment values if they have been obtained up to the end of the endpoint-specific follow-up period X, as defined in [Table 6.7: 1](#) below. Measurements taken after the last intake of study medication and after the endpoint-specific follow-up period X will be considered off-treatment values for the treatment in question.

Table 6.7: 1 Endpoint-specific follow-up period X for assignment to active treatment

Treatment phase	Endpoint(s)	Last day of assignment to treatment phase (days after study drug stop date)
Open-label ramipril run-in (for patient not subsequently randomised)	GFR	1
	HbA1c	7
	Waist circumference	7
	All other further endpoints	1
	Adverse events	7
	Safety laboratory measurements	3
Open-label ramipril run-in (for patient subsequently randomised)	GFR	0
	HbA1c	0
	Waist circumference	0
	All other further endpoints	0
	Adverse events	0
	Safety laboratory measurements	0
Double-blind treatment (both periods)	GFR	1
	HbA1c	7
	Waist circumference	7
	All other further endpoints	1
	Adverse events	7
	Safety laboratory measurements	3

Visit window definitions for each treatment phase and time point, based on the relevant anchor date to define relative days, are shown in [Table 6.7: 2](#). These visit windows will be used in all analyses and summaries of endpoints at specific time points.

Further details on the specific handling of GFR values outside these visit windows, or of insufficient washout, with regard to IPDs and PPS analysis are given in [Section 6.2](#).

Table 6.7: 2 Time windows for scheduled visits

Nominal visit number B	Treatment phase	Visit label	Anchor date	Planned days	Time window (actual days from anchor date)	
					Start	End
8	Run-in (OL Ramipril)	OL Week 4	First ramipril administration	28	15	42
11	Period 1 (Empa 25mg/Placebo)	Week 4	First period 1 medication administration	28	15	42
12	Washout	NA	Last period 1 medication intake	28	15 A	42
15	Period 2 (Placebo/Empa 25mg)	Week 4	First period 2 medication administration	28	15	42

A Note that the washout period itself commences on the (X+1)th day after visit 11 so at least (X+1) days are required for there to be any washout period at all.

B Any values from EOT visits also need to be assigned to the correct treatment phase and appropriate visit window, in addition to values from nominal visits 8, 11, 12 and 15.

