## 6. GENERAL ANALYSIS DEFINITIONS

### 6.1 TREATMENTS

There will be a maximum of eight treatment periods for patients included in this trial: screening, Ramipril run-in, ramipril post-treatment, on-treatment (crossover) period 1 (with either empagliflozin or matching placebo), treatment x wash-out period, on-treatment (crossover) period 2 (with either empagliflozin or matching placebo), treatment x post-treatment period, and post-study. The definitions of each of these treatment periods are defined in [Table 6.1: 1](#) below. (**Note:** ‘double-blind medication’ refers to either empagliflozin or placebo and ‘any study medication’ refers to either ramipril, empagliflozin or placebo.)

Table 6.1: 1 Definitions of treatment periods

Period	Start date	End date
Screening	Informed consent	Start date of open-label ramipril run in period – 1 day
Ramipril run-in	First administration of open-label Ramipril	Start date of DB on-treatment period 1 – 1 day, or, Date of last intake of open-label ramipril + x (for those patients who were not treated with DB medication)
Ramipril post treatment#	Date of last intake of open-label ramipril + x + 1	Last study contact.
On-treatment period 1 ‘Period 1’ or ‘Empa 25mg’ or ‘Placebo’	Date of first administration of first DB medication	Date of last administration of first DB medication + x
Treatment x washout ‘Empa 25mg washout’ or ‘Placebo washout’	Date of last intake of first DB medication + x + 1	Start date of second DB on-treatment period – 1 day. Date is not defined for patients who did not receive DB medication in period 2
On-treatment period 2 ‘Period 2’ or ‘Empa 25mg’ or ‘Placebo’	Date of first administration of second DB medication	Date of last administration of second DB medication + x
Treatment x post treatment ‘Empa 25mg post treatment’ or ‘Placebo post treatment’	Date of last administration of DB medication + x + 1 day	Date of last study contact + 1 day
Post study	Date of last study contact + 1 day	Date of trial database lock. Date is not defined for a patient that is lost to contact whilst still receiving study medication.

For efficacy, x=1 day, for AE x=7 days and for laboratory parameters x=3 days as defined in [Section 6.7](#).

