# This time period is defined only for patients treated with open label ramipril but not DB medication (and therefore not in the TS).

For certain efficacy and safety analyses, as well as for laboratory data, measurements will still be considered on-treatment during a follow-up period of e.g.  $X = 7$  days ([see Section 6.7](#)). This will be applied programmatically where needed and not used in trial database set up; for the latter  $X = 0$  will be used.

The efficacy analyses will follow the intention-to-treat (ITT) principle in assigning patients to treatment groups, i.e. patients will be analysed as randomised.

Safety analyses will assign patients to the treatment group as treated. If a patient erroneously receives the wrong trial medication, the patient will be analysed according to the actual trial medication received. In addition, AEs with an onset during the time of the incorrect study treatment will be tabulated and listed separately.

The open-label ramipril run-in period will be labelled as the single treatment arm “OL Ramipril” on relevant outputs.

The first and second double-blind on-treatment periods will be labelled “Empa 25mg” and “Placebo” according to the medication assigned to or taken in that period (note: the additional background ramipril will not, therefore, form part of the double-blind treatment labels).

Demographic and baseline summaries will be presented by assigned treatment sequence, which will be labelled as “Empa25/Pbo” and “Pbo/Empa25” respectively. On these summaries a “Total” column will be presented, which is the sum of the number of patients in the two treatment sequence columns.

In general, on efficacy and safety tables presenting double-blind treatment, a “Total” column will not be added, noting in any case that for a crossover design, “Total” is not the sum of the number of patients displayed under “Empa 25mg” and “Placebo”.

A limited number of exploratory outputs may also display the crossover period as well as the double-blind treatment. For this purpose, the labels used will be “Period 1” and “Period 2”.

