#### 7.8.2 Laboratory data

For continuous safety laboratory parameters standardised and normalised values will be derived, as well as the differences to screening baseline for the open-label ramipril run-in period, and to both screening and randomisation baselines for the double-blind period.

If the period baseline for a particular laboratory parameter is available (see definition in [Section 6.7](#)), then this will be used, in place of the randomization baseline value. Throughout the remainder of this section, however, randomization baseline will be referred to.

The process of standardisation and normalisation, as well as standard analyses for safety laboratory data, are described in the BI guidance for the Display and Analysis of Laboratory Data ([4](#)). All analyses considering multiple of times upper limit of normal (ULN) will be based on original and not normalized data.

Analysis of further endpoints derived from specific laboratory parameters is described in [Section 7.6](#).

Results of laboratory analyses will be presented based on both SI units and US conventional units.

Screening baseline for safety laboratory parameters will be the last available measurement before the start of OL ramipril treatment. Randomisation baseline for safety laboratory parameters will be the last available measurement before the start of double-blind treatment. Unless otherwise specified, laboratory measurements taken up to 3 days after the last administration of study drug will be considered as on-treatment (see [Section 6.1](#) and [Section 6.7](#)).

Only patients with at least one available on-treatment value will be included in the analysis of an individual laboratory parameter. All individual data will be presented in listings.

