##### 7.8.2.1 General laboratory evaluation

Laboratory values will be compared to their reference ranges and frequency tables will be provided for the number of patients within and outside the reference range at baseline and the

last measurement on treatment. Descriptive statistics will be provided by treatment for baseline, on-treatment values and for changes from baseline based on normalised values, as well as on the basis of standardized values for parameters with an incomplete reference range (e.g. lipids).

Descriptive statistics will in addition be calculated for the changes from screening and randomisation baselines in haematocrit over time, including during the follow-up period. In particular, statistics will be provided for last-value on-treatment, follow-up, change from baseline for last on-treatment value and follow-up, and change from last on-treatment assessment to follow-up.

Frequency tables will summarise the number of patients with potentially clinically significant abnormalities.

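### Does the washout sentence in SAP Section 6.7, which leaves out the follow-up period X, remove period-1 samples from the on-treatment summaries?

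*SAP*

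**What the plan says.** Section 6.7 first sorts measurements by when they were taken: before any study drug, during the ramipril run-in, or between the two double-blind periods. For the last group it states: "Measurements taken after the last intake of the first double-blind medication but before the intake of the second double-blind medication will be considered washout values". The next paragraph assigns treatment status. Values after the first intake of any study drug "will be considered on-treatment values if they have been obtained up to the end of the endpoint-specific follow-up period X", and "Measurements taken after the last intake of study medication and after the endpoint-specific follow-up period X will be considered off-treatment values". Table 6.7: 1 gives X for both double-blind periods: GFR 1 day, HbA1c 7, waist circumference 7, all other further endpoints 1, adverse events 7, safety laboratory 3.

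In Section 6.1, Table 6.1: 1 starts the washout period at "Date of last intake of first DB medication + x + 1". The text after it says of X: "This will be applied programmatically where needed and not used in trial database set up; for the latter", the value is 0.

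Section 7.8.2 repeats the laboratory rule: "laboratory measurements taken up to 3 days after the last administration of study drug will be considered as on-treatment". Footnote A of Table 6.7: 2 also starts washout on day X + 1, but counts from visit 11. Its own table row counts from the last period-1 intake.

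**The concern.** Two neighbouring paragraphs of one section seem to give the same sample two statuses. A laboratory sample drawn two days after the last period-1 dose is a washout value under the first and an on-treatment value under the second. The SAP does not say which prevails, and the first sentence is not marked as the X = 0 database convention of Section 6.1.

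If a programmer let the washout label override, period-1 samples drawn after the last dose and within 3 days of it would leave the laboratory outputs that depend on treatment status and are not tied to a visit window. These are the inclusion rule ("Only patients with at least one available on-treatment value will be included in the analysis of an individual laboratory parameter"), the last-measurement and on-treatment tables of Section 7.8.2.1, and the eGFR shift table and creatinine-doubling summary of Section 7.8.2.4. A minimum over fewer values cannot be lower, and a count of patients with a doubling cannot be higher. Any error in those two outputs would therefore understate a renal signal, and in period 1 only, because period 2 has no matching sentence. The sentence speaks of measurements in general, so visit 11 GFR also has to be checked.

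**Working it through.** No sample size, power or alpha figure is involved. The check sets the rules side by side and asks which one each output uses.

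**1. Size of the mismatch.** Let L be the day of the last period-1 intake. Table 6.1: 1 starts washout at L + X + 1; the Section 6.7 sentence starts it directly after the dose on day L. With X from Table 6.7: 1:

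| Data | X | Washout start, L + X + 1 | Days after L with both labels |
|---|---|---|---|
| GFR, other further endpoints | 1 | L + 2 | 1 |
| Safety laboratory | 3 | L + 4 | 1 to 3 |
| HbA1c, waist circumference | 7 | L + 8 | 1 to 7 |
| Adverse events | 7 | L + 8 | 1 to 7 |

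Values taken after the dose on day L itself are also covered. The adverse-event row applies only if events are counted as measurements.

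**2. Are the labels exclusive?** No. The first paragraph gives a position in time. The second gives treatment status and covers ramipril as well as the double-blind drugs. A sample taken during run-in is a run-in value under the first and an on-treatment value under the second, with no conflict. Nothing in the washout sentence withdraws on-treatment status, and the second paragraph grants it up to the end of X.

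**3. Which rule does each output use?**

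- *Laboratory.* Every output listed in the concern lies within Section 7.8.2. They select on treatment status, not on the absence of a washout label, and Section 7.8.2 fixes that status at 3 days. A sample at L + 2 has 2 ≤ 3 and stays in.
- *Adverse events.* Section 7.8.1.1 uses the periods of Table 6.1: 1 and restates the 7 days.
- *Week-4 GFR.* Section 5.1 accepts every recorded value except those outside the visit window. The visit 11 window is days 15 to 42 from the **first** period-1 dose, so the last dose does not enter. For example, with the last dose on the planned day 28 and GFR measured one day later, the value falls on day 28 + 1 = 29, inside 15 to 42.
- *Other time-point endpoints.* Section 6.7 applies the same windows to all summaries at specific time points.

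**4. Footnote A.** The largest X is 7, so X + 1 = 8 days. The tabulated washout window opens on day 15 after the last period-1 intake. Since 8 < 15, the footnote's anchor does not move that window. The two anchors coincide when the last dose falls on the visit 11 date, or when a missing stop date is imputed as that date under Section 6.6.3.

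**The case for a change.** The strongest case for a change is that the washout sentence reads like an operative rule. The neighbouring sentence on run-in values agrees with Table 6.7: 1, which sets X = 0 for run-in patients who are later randomised, so a reader may expect the washout sentence to agree too. It stands in the section that defines analysis windows, and no order of precedence is given. Footnote B of Table 6.7: 2 also requires end-of-treatment values to be assigned to the correct phase as well as to a window, so the window alone does not settle every case.

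The mismatch in wording stands. The consequence does not. The tables holding X are cited wherever status matters: Section 6.1 takes its x values from Section 6.7, Section 7.8.1.1 cites both Table 6.1: 1 and Table 6.7: 1, and Section 7.8.2 cites Sections 6.1 and 6.7. Table 6.7: 1 names both double-blind periods. For an end-of-treatment value, the phase follows from those same tables.

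One further loose end is that the note under Table 6.1: 1 gives x = 1 for efficacy, while Table 6.7: 1 gives 7 for HbA1c and waist circumference. The note defers to Section 6.7, so the table governs.

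**Conclusion.** The concern does not call for a change. The sentence leaves out X, and footnote A names a different anchor from its table row; both are drafting slips. The disputed interval is at most 3 days for laboratory data and 1 day for GFR, and within it each class of output has a more specific rule that gives the intended answer. Rewording would be tidier but would alter no analysis.

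This rests on two assumptions. Programmers take laboratory status from Section 7.8.2 and adverse-event periods from Table 6.1: 1, as those sections direct. The further endpoints are summarised at time points, so the visit windows of Section 6.7 apply to them. The SAP does not give the timing of period-1 samples relative to the last dose, so the number of values in the disputed interval cannot be derived; it could be none. The conclusion does not depend on that number, because such values stay on treatment whatever their count.
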